## REVISION HISTORY

Revisions to Version 4.0 dated 08 February 2021

Summary of Change	Rationale	Affected Protocol Sections
Added statement that study drug infusions should not begin if the subject's mean arterial pressure (MAP) is less than 65 mmHg	DMC recommendation	

• Synopsis

• Section 9.2

• Section 10.2.2

• Appendix 1

Added clarification to SAE reporting	To provide sites with further guidance on SAE reporting for this patient population	

• Section 10.5.1

Revisions to Version 3.0 dated 30 June 2020

Summary of Change	Rationale	Affected Protocol Sections
Updated estimated enrollment period and studied period	To be accurate with current study status	

• Synopsis

Updated Inclusion Criteria #1 to allow sites to use their standard of care testing method for SARS-CoV-2 Infection	To be consistent with site's standard practice	

• Synopsis

• Section 7.1

Revised Inclusion Criteria #3 to require FiO 2 of >/= 50% instead of >/= 60%	To allow inclusion of additional subjects who still will fit the critically ill patient population	

• Synopsis

• Section 7.1

Added clarification to Exclusion Criteria #7 and prohibited medication section regarding subject participation in concurrent clinical trials	To provide additional guidance to sites on subject inclusion	

• Synopsis

• Section 7.2

• Section 8.2

Added window of +/- 2 hours for study drug dosing	To provide additional guidance for subject dosing	

• Synopsis

• Section 6.1

• Section 6.2

• Section 10.2.2

• Appendix 1

Revised CYP2D6 requirements and removed from prohibited medications	To allow investigators to use their judgement in the use of these medications	

• Synopsis

• Section 8.1

• Section 8.2

Revised to require direct bilirubin, CRP, and triglycerides at baseline only unless clinically indicated.	To be consistent with site's standard practice	

• Section 10.1.2

• Appendix 1

Revised to require SOFA score only while subjects are in the ICU.	To align with standard practice	

• Synopsis

• Section 10.2.3

• Appendix 1

Added language around timing of first two doses	To provide additional guidance for subject dosing	

• Appendix 1

Revised to require Hematology/Chemistry samples	To be consistent with site's standard practice	

• Appendix 1

Summary of Change	Rationale	Affected Protocol Sections
after completion of treatment only if clinically indicated.		
Clarified PK collection timepoints	To emphasize samples only need to be collected pre/post first infusion on Days 1 and 3	• Appendix 1
Added language to allow post-discharge follow-up visits to be done remotely (virtual/phone).	To provide flexibility to study subjects depending on their post discharge status.	• Appendix 1
Updated Schedule of Assessments: 
 
- to specify that Apache IV score only needs to be done once at screening/baseline and the worst value in the past 24 hours should be recorded.
 
- to remove the collection of daily fluid balance after treatment discontinuation
 
- to specify that if multiple labs are done in one day, the worst value should be recorded.
 
- to revise requirement of viral load testing to screening/baseline, Day 7, and Day 14
 
- to revise requirement of cytokine blood draw to screening/baseline, Day 7, and Day 14
 
- to revise “each additional day in hospital” to “each additional day in ICU”
 
- to revise “after discharge from hospital” to “after discharge from ICU”
 
	To provide additional guidance to sites	• Appendix 1
Other editorial changes have been made throughout	To correct administrative errors and ensure content accuracy and consistency.	• Throughout

## 1. SYNOPSIS

Name of Sponsor/Company: Galera Therapeutics, Inc.	
Name of Investigational Product: GC4419	
Name of Active Ingredient: avasopasem manganese	
Title of Study: A Pilot, Randomized, Placebo-Controlled Trial of GC4419 (avasopasem manganese) in Patients with Critical Illness Due to SARS-CoV-2 Infection (COVID-19)	
Number of Study Center(s): up to 10	
Estimated Enrollment Period: 9-12 months	
Studied period: First patient enrolled: September 2020 Estimated date last patient completed assessment for primary endpoint: September 2021	Phase of development: 2
Background: 
SARS-CoV-2/COVID-19: Approximately 20% of people with confirmed, symptomatic COVID-19 disease, due to infection with the SARS-CoV-2 virus, will develop viral pneumonia requiring hospitalization. These patients exhibit respiratory compromise that can be characterized as severe (demonstrating dyspnea, hypoxia, and/or extensive lung opacities on chest x-ray); or critical, with respiratory failure, which may be accompanied by shock or multiorgan dysfunction). Approximately 25% of hospitalized patients, comprising approximately 5% of all patients with symptomatic infection, will have critical disease as described herein. Critical disease often manifests as a clinical picture consistent with the acute respiratory distress syndrome (ARDS), although information is still being obtained regarding the pathophysiology and pathophysiology of pulmonary compromise associated with SARS-CoV-2, compared with ARDS related to other causes. Retrospective series suggest that, after a variable initial course of disease, dyspnea begins approximately 6-7 days after the first symptoms of infection, with swift progression to frank respiratory failure/ARDS 2-3 days thereafter. Intensive care is often required for 14 days or more, and more than one attempt at ventilator weaning may be required before eventual extubation. Comorbidity among these critically ill patients includes renal, cardiac, and hepatic damage as well as hypotension requiring vasopressor treatment (Yang et al, 2020). Mortality for critically ill patients, highest among the elderly or those with significant prior concomitant conditions, has been reported to be on the order of 50-60% (Yang et al, 2020; Wu et al 2020). The IHME has recently projected that, assuming full social distancing throughout the United States through May 2020, nationwide needs for hospital beds and ICU beds will exceed national capacity (https://covid19.healthdata.org/projections, accessed 15 April 2020, 12 noon EDT) Further, pending effective treatments or vaccine(s), potential remains for recurrent waves of infection and the attendant needs for hospital resources.
	

The proximate cause of ARDS in COVID-19 disease appears to be an inflammatory response, including a cytokine "storm," complicating the initial infection and producing pneumonitis. Such responses are accompanied by production of large amounts of superoxide by activated macrophages and neutrophils. It is this superoxide free radical which both initiates and sustains the inflammation, and which is produced in amounts sufficient to overwhelm the normal capacity of endogenous superoxide dismutase (SOD) enzymes to remove it. Similarly, superoxide is critical to the development of shock characterized by hypotension that is non-responsive to vasopressor (catecholamines such as norepinephrine) therapy. In the latter case, superoxide deactivates endogenous catecholamines, reacting with them via a free radical autoxidation cascade producing toxic products called "adrenochromes" (Macarthur et al, 2000). This process also results in hyporeactivity to exogenously-administered catecholamines, producing hypotension that is refractory to vasopressor treatment.

Avasopasem manganese (avasopasem): Avasopasem manganese is a highly selective, small molecule (MW 483) mimetic of naturally occurring superoxide dismutase (SOD) enzyme, which, like native SOD, converts superoxide to hydrogen peroxide and molecular oxygen specifically and selectively, at an enzymatic rate comparable to that of the native SOD. In disease states characterized by excessive superoxide production, administration of avasopasem replaces or augments deficient or insufficient endogenous SOD capacity. Accordingly, avasopasem and related active dismutase mimetics have demonstrated ability to protect tissues from superoxide-mediated damage in laboratory studies and in the clinic. Results from *in vivo* models include: reduced zymosan-induced lung neutrophil infiltration, lipid peroxidation and lung injury, and mortality (Cuzzocrea et al, 2004); in the bleomycin intratracheal mouse model, reduced lung inflammatory infiltrates and alveolar epithelial apoptosis (Herzog, 2014); in a chronic asthma guinea pig model, reduced neutrophil infiltrate, lipid peroxidation and alveolar epithelia apoptosis (Masini et al, 2005); and in a lung focal irradiation mouse model, reduced late stage pulmonary fibrosis (Sishc et al, 2018). Results from animal studies also include reduction of *E. coli*-induced hypotension, vascular hyporeactivity to catecholamines, and mortality in septic shock (Macarthur et al, 2003), and decreased levels of proinflammatory cytokines such as TNF $\alpha$ , IL-1 $\beta$  and IL-6 (Cuzzocrea et al 2004; Macarthur et al, 2003), with increase in the anti-inflammatory cytokine IL-10 (Macarthur et al, 2003). In these studies, dismutase mimetic was administered continuously or repeatedly over several hours after challenge with zymosan or *E. coli* (Cuzzocrea et al 2004; Macarthur et al, 2003). In a hamster model, avasopasem reduced severe oral mucositis (Sonis, unpublished data, GC4419 Investigator's Brochure), supporting clinical trials of GC4419 to reduce radiation-induced severe oral mucositis. In Phase 1-2b clinical trials (Anderson et al 2018; Anderson et al 2019), GC4419 reduced the incidence, severity, and duration of severe oral mucositis produced from the superoxide generated due to concurrent chemoradiotherapy for head and neck cancer, with an acceptable safety profile, and a confirmatory Phase 3 trial (NCT03689712) in this indication is underway under Breakthrough Therapy Designation from FDA.

GC4419 has been safely administered to over 300 human subjects, with the Phase 3 oral mucositis trial testing 90 mg by 60-minute IV infusion, repeated each weekday, prior to standard radiotherapy, for 7 weeks—a total of up to 35 doses. Toxicity attributable to GC4419 has been limited to transient, infusion-related mild hypotension and postural symptoms, and mild circumoral paresthesia, attributable to reversible potentiation of nitric

oxide. These effects appear to be related to the  $C_{max}$  (which occurs at the end of the IV infusion), and are further limited with lower doses or prolonged infusion time at a given dose, with mild orthostatic lightheadedness reported in 6 of 72 healthy volunteers who have received 27 mg of GC4419 over 60 minutes, and 5 of 34 healthy volunteers who received 30 or 51 mg of GC4419 IV over 15 minutes. Adverse events observed in the oral mucositis trials have been those observed with the underlying standard regimen of radiation therapy plus cisplatin, and in a placebo-controlled randomized Phase 2b trial, the adverse event profiles for subjects receiving GC4419 or placebo were similar.

No effect on the QT interval was found in a precision QT clinical trial of GC4419 at a dose of 51 mg IV over 15 minutes, a dose and schedule at which  $C_{max}$  exceeds that produced after a 90 mg/60-minute infusion of GC4419.

Nonclinical GLP toxicology studies of avasopasem in rats and dogs have shown no abnormal histopathologic findings except for injection-site reactions after subcutaneous administration. These studies include 6-month chronic toxicology in rats (final report pending). A 9-month chronic toxicology study in dogs is in progress in the in-life phase. Results of GLP toxicological studies support dosing of GC4419 at a total daily dose of up to 198 mg for up to 14 days.

GC4419 has a plasma half-life of approximately 2 hours, reaching maximum concentration at the end of IV infusion and declining in a bi-exponential fashion thereafter. Plasma exposure is approximately dose-proportional. In past clinical trials, GC4419 has been quantifiable in plasma up to approximately 24 hours after a 60-minute IV infusion, with minimal accumulation in plasma with repeated daily dosing. Non-clinical data indicate a longer half-life of GC4419 in tissues, with rapid entry into cells related to  $C_{max}$  and slower release from cells.

GC4419 is eliminated by GI and renal routes. Human volunteer studies of GC4419 in the setting of compromised renal or hepatic function are in progress. There has been no apparent nephrotoxicity or hepatotoxicity of GC4419 in human clinical trials.

Rationale for the present study: The pathogenesis of severe-to-critical pulmonary disease complicating SARS-CoV-2 infection—and, when it occurs, the pathogenesis of attendant shock—along with the mechanism and available nonclinical and clinical data with GC4419, suggest that GC4419 could attenuate or reduce the risk of ARDS and the need for mechanical ventilation, and attenuate shock, in people suffering from them due to SARS-CoV-2.

The present study is intended as an initial assessment to confirm the safety of GC4419 in COVID-19 patients with critical respiratory illness. Hospitalized subjects whose respiratory function has deteriorated to the point where mechanical ventilation is needed will be studied. Subjects will be randomized in a 1:1 ratio to receive either GC4419 or placebo plus standard supportive care.

Upon review of results from this trial, future trials to treat COVID-19 patients with GC4419 earlier in the course of disease—e.g., in the setting of worsening hypoxemia and increasing requirement for supplemental oxygen short of mechanical ventilation—may be considered.

## **Objectives:**

Primary:

- To evaluate 28-day all-cause mortality/overall survival

Secondary (all through the same 28 days as for the primary endpoint):

- To evaluate the safety of avasopasem in the study population
- To evaluate the frequency of successful ventilator weaning
- To evaluate the number days alive and intensive care-free
- To evaluate the number of days alive and ventilator-free
- To evaluate the number of days with minimum SpO2/FIO2 ratio or PaO2/FIO2 > 300
- To evaluate the number of days alive without vasopressor/catecholamine support
- To evaluate the incidence of mean arterial pressure < 65 mmHg on optimized vasopressor therapy
- To evaluate the number of days alive with a SOFA score of 6 or less
- To evaluate the percentage of subjects with an increase in mean arterial pressure of 10 mm Hg or more at the end of more than one infusion of GC4419

Exploratory:

- To assess levels of circulating cytokines IL-6, TNF-alpha, IL-1 beta, IL-10
- SARS-CoV-2 viral load by PCR testing for viral RNA
- To assess the plasma exposure to GC4419 in the study subjects

### **Methodology:**

COV-4419-201 will be a randomized study to evaluate GC4419 administered IV to subjects with confirmed SARS-CoV-2 infection and critical pulmonary disease.

To help ensure balanced randomization, subjects will be stratified at randomization for age < 60 years vs >=60 years

All subjects will receive standard supportive care according to the policies of the treating institution.

Subjects will be randomized in a 1:1 ratio to receive either:

- GC4419 by IV infusion q 12 hours (+/- 2 hours) for 7 days, plus standard supportive care, or
- Placebo by IV infusion q 12 hours (+/- 2 hours) for 7 days, plus standard supportive care

### Rationale for GC4419 dosing plan:

- Extensive clinical experience in cancer patients supports the safety of 90 mg of GC4419 administered over 60 minutes for 35 doses (M-F, up to 7 weeks) concurrently with chemoradiotherapy.
- Cmax-related transient mild hypotension and orthostasis has been observed at the current 90 mg/60-minute infusion schedule, but this is less frequent with lower doses.
- Therefore, administering 90 mg of GC4419 IV over 180 minutes (3 hours) is expected to provide an additional margin of safety.
- The plasma half-life of GC4419 is approximately 2 hours.
- Pharmacokinetic results to date do not indicate significant plasma accumulation of GC4419 with repeated dosing.

- Results of GLP animal toxicology studies support a total daily dose of GC4419 up to 198 mg, administered for up to 14 days (compared with planned 7 days in the current study).
- Administration of a related dismutase mimetic to rats in the zymosan and *E. coli* sepsis models was performed over a period of several hours after challenge with zymosan or *E. coli*. Moreover, the persistent superoxide production is expected to be associated with the ongoing COVID-19 disease process. Accordingly, a dosing schedule that maintains extracellular concentrations of GC4419 as much as possible and feasible may be desirable.

In light of the above, subjects will receive, in a blinded fashion, either GC4419, 90 mg intravenously, or placebo, administered over 3 hours (180 minutes), repeated every 12 hours (+/- 2 hours) for 7 consecutive days.

Subjects requiring renal dialysis should not have that procedure performed at any time during GC4419/placebo infusion and until at least 2 hours after infusion. If continuous renal replacement therapy is required for >24 hours, dosing with blinded GC4419/placebo will be discontinued.

Adverse Events and Serious Adverse Events will be assessed daily during dosing of GC4419/placebo, then daily during hospitalization and weekly after hospital discharge, for a total of 30 days after the last dose of GC4419/placebo. Post-dosing AE assessment may be done on an outpatient basis for subjects who are discharged from the hospital.

Ongoing safety results will be monitored by an independent Data Monitoring Committee (DMC) that will operate under a specific DMC charter separate from this protocol document.

**Number of patients (planned):**

Approximately 50 subjects, 25 receiving GC4419 and 25 receiving placebo.

**Diagnosis and main criteria for inclusion:**

Inclusion Criteria:

1. Laboratory-confirmed SARS-CoV-2 infection as determined by a positive PCR test documented prior to randomization:
  - a. Performed on a swab sample from the nasopharynx of a non-intubated subject or pulmonary secretions from an intubated subject per site's standard practice
  - b. Analyzed by a commercial, local, or public health laboratory
  - c. A duplicate swab will be retained for subsequent confirmation at a Central Laboratory
2. Requirement for intensive inpatient hospital care
3. Acute hypoxemic respiratory failure typifying ARDS, as indicated by:
  - a.  $\text{PaO}_2/\text{FiO}_2 < 300 \text{ mm Hg}$ , or  $\text{SpO}_2 < 94\%$  on  $\text{FiO}_2 \geq 50\%$  with bilateral pulmonary infiltrates along with respiratory distress and increased work of breathing requiring intubation and invasive mechanical ventilation, OR
  - b. Non-invasive mechanical ventilation with  $\text{SpO}_2 < 94\%$  on  $\text{FiO}_2 \geq 50\%$
4. Adequate liver function as indicated by:
  - a. Total bilirubin  $\leq 1.5 \times$  upper-normal limit (ULN)
  - b. Aspartate aminotransferase (AST) and alanine aminotransferase (ALT)  $\leq 2.5 \times$  ULN
5. Age 18 years or older

6. Serum or urine pregnancy test negative for females of childbearing potential
7. Properly obtained informed consent obtained from subject or legally authorized representative

**Exclusion Criteria:**

1. Expected survival for less than 48 hours after randomization
2. Child-Pugh stage C hepatic impairment and/or portal hypertension secondary to cirrhosis
3. Stage IV chronic kidney disease or end-stage kidney disease on maintenance hemodialysis
4. Requirement for extra-corporeal membrane oxygenation (ECMO)
5. Acute Myocardial Infarction (AMI)
6. Active bleeding requiring transfusion
7. Concurrent participation in another clinical trial of experimental treatment for SARS-CoV-2

**Note:** Concurrent participation in any study of an approved treatment, or a product with Emergency Use Authorization for COVID treatment, is permitted if the Principal Investigator attests that the mechanism of the EUA product is not expected to interfere with the mechanism of GC4419 and that completion of study requirements for this protocol will not be compromised

8. Female patients who are pregnant or breastfeeding
9. Requirement for concurrent treatment with nitrates

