#### **Concomitant Medications/Treatments:**

Investigators may prescribe any concomitant medication or supportive therapy deemed medically indicated for the care of the subject, with exception of the following prohibited medications/treatments:

- Nitrates, phosphodiesterase type 5 (PDE 5) inhibitors (e.g., sildenafil, tadalafil, or similar agents) or other concomitant drugs that in the judgment of the treating investigator could create a risk of a precipitous decrease in blood pressure are prohibited until at least 24 hours after the last dose of blinded GC4419/placebo.
- Concurrent participation in a clinical trial of investigational therapy for SARS-CoV-2.
  - *Other approved or unapproved agents for SARS-CoV-2, including drug or biologic therapy including immunomodulatory treatments, administered on an expanded access, compassionate care, off-label, or emergency access basis may be administered. Use as part of another, concurrent clinical trial may be considered provided the site principal investigator determines that the mechanism of the other treatment is not expected to interfere with the mechanism of GC4419, and that completion of study requirements for this protocol will not be compromised.*
  - *Examples of acceptable concurrent medications under this provision include remdesivir, hydroxychloroquine (alone or with azithromycin) convalescent plasma, and other drug or biologic treatments for SARS-CoV-2 as long as not part of a clinical trial other than the present trial.*

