### **7.5. Subject Withdrawal Criteria**

In accordance with the Declaration of Helsinki, a subject has the right to withdraw from the study at any time for any reason. The Investigator may also, at his/her discretion, discontinue a subject from participating in this study at any time. Additionally, study treatment may be discontinued for any of the following reasons:

- AE
- Medical requirement to administer a contra-indicated medication
- Subject non-compliance
- Subject has a confirmed positive serum pregnancy test
- Discontinuation of the study at the request of the Sponsor

The primary reason for ceasing treatment will be clearly documented in the subject's medical record and recorded on the appropriate CRF page. A subject who permanently discontinues treatment with GC4419/placebo will not be allowed to be retreated.

If a subject discontinues study drug as a result of an AE or serious adverse event (SAE), every attempt should be made to keep the subject in the study and continue to perform the required

study-related follow-up and procedures. If this is not possible or acceptable to the subject, the subject may be withdrawn from the study.

If a subject withdraws consent, additional details about the reasons for that decision will be sought and documented.

Withdrawn subjects will not be replaced.

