### **8.2. Prohibited Medications**

Investigators may prescribe any concomitant medication or supportive therapy deemed medically indicated for the care of the subject, with exception of the following prohibited medications/treatments:

- Nitrates, phosphodiesterase type 5 (PDE 5) inhibitors (e.g., sildenafil, tadalafil, or similar agents) or other concomitant drugs that in the judgment of the treating

investigator could create a risk of a precipitous decrease in blood pressure are prohibited until at least 24 hours after the last dose of blinded GC4419/placebo.

- Concurrent participation in a clinical trial of investigational therapy for SARS-CoV-2.
  - *Other approved or unapproved agents for SARS-CoV-2, including drug or biologic therapy including immunomodulatory treatments, administered on an expanded access, compassionate care, off-label, or emergency access basis may be administered. Use as part of another, concurrent clinical trial may be considered provided the site principal investigator determines that the mechanism of the other treatment is not expected to interfere with the mechanism of GC4419, and that completion of study requirements for this protocol will not be compromised.*
  - *Examples of acceptable concurrent medications under this provision include remdesivir, hydroxychloroquine (alone or with azithromycin) or convalescent plasma, and other drug or biologic treatments for SARS-CoV-2 as long as not part of a clinical trial other than the present trial.*

Subjects who receive prohibited medications will not automatically be removed from the study; however, administration of a prohibited medication is a significant deviation from the protocol and must be reported to the Medical Monitor as soon as possible and the presiding IRB/IEC/REB (per institutional guidelines). The decision for study continuation or discontinuation will be made at that time on a case-by-case basis and in consideration of the clinical requirement and circumstances.

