### **12.3. Protocol Compliance**

The investigator is responsible for ensuring the study is conducted in accordance with the procedures and evaluations described in this protocol.

In general, major protocol deviations include deviations from inclusion/exclusion criteria, from concomitant medication restrictions, and from any other protocol requirement that could, at least hypothetically, result in significant risk to the subject and/or affect the outcome of the clinical trial. Major protocol deviations will be noted in the final Clinical Summary Report.

A minor deviation is defined as non-adherence to the protocol procedures or schedule as defined by the protocol or the primary endpoint that does not place the subject at any added or significant risk or affect the data quality or the outcome of the clinical trial (eg, a missed procedure, an out-of-window site visit).

Only subjects who meet protocol-defined eligibility criteria may be enrolled in this clinical trial. If any protocol eligibility criteria or procedures are unclear, the investigator or investigational site personnel should contact the Clinical Research Associate. If the question requires medical interpretation, the sponsor's medical monitor should be consulted. All protocol deviations should be reported to the IRB/IEC according to the standard practices of the investigational site and applicable regulatory requirements.

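### Exclusion 9 bars patients who require nitrates but not those who require PDE5 inhibitors, although Section 8.2 prohibits both classes together for the same blood-pressure risk

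*Combined protocol and SAP*

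**What the plan says.** **Entry.** The Synopsis and protocol Section 7.2 each list nine exclusion criteria. The ninth is "Requirement for concurrent treatment with nitrates". None of the nine mentions PDE5 inhibitors.

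**On study.** The Synopsis (Concomitant Medications/Treatments) and Section 8.2 prohibit "Nitrates, phosphodiesterase type 5 (PDE 5) inhibitors (e.g., sildenafil, tadalafil, or similar agents) or other concomitant drugs". The rest of that sentence gives both the reason and the end of the restriction, and leaves the last group to clinical judgement: "investigator could create a risk of a precipitous decrease in blood pressure are prohibited until at least 24 hours after the last dose".

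**If the rule is broken or cannot be kept.** Section 8.2 says that "administration of a prohibited medication is a significant deviation from the protocol". It must be reported to the Medical Monitor, and whether the subject continues is decided individually in light of the clinical need. Section 7.5 lists "Medical requirement to administer a contra-indicated medication" among the reasons for stopping study treatment and adds: "A subject who permanently discontinues treatment with GC4419/placebo will not be allowed to be retreated". It also says: "Withdrawn subjects will not be replaced".

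**Mechanism.** Section 9.1 attributes the adverse effects expected with GC4419 to a temporary boost to nitric oxide. Mild hypotension is one of the effects it names.

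**The concern.** Two drug classes are prohibited in one sentence, for one hazard, with a study drug whose expected toxicity works through nitric oxide. Only one of them is also a bar to entry, and the protocol gives no reason for the difference. If the Section 8.2 prohibition were thought sufficient alone, exclusion 9 would not be needed for nitrates either. If it is not sufficient for nitrates, nothing in the documents shows why it is sufficient for PDE5 inhibitors.

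What is at stake is the position of a patient who needs a PDE5 inhibitor. The patient can be enrolled into a trial that forbids the drug throughout dosing, and the conflict comes to light only when someone has to choose between the required drug and the study drug. Screening could prevent this, since medications are already reviewed then (Section 10.2.1 and Appendix 1).

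**Working it through.** The plan gives no figure to reproduce here. The check is mainly a comparison of texts, with one short calculation.

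**1. The two lists side by side**

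| Drug class | Exclusion 9 (Synopsis, 7.2) | Prohibition (Synopsis, 8.2) |
|---|---|---|
| Nitrates | Named | Named |
| PDE5 inhibitors | Not named | Named |
| Other drugs judged by the investigator to carry the same risk | Not named | Included by judgement |

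The third row cannot sensibly be an entry criterion, because it depends on individual judgement. The second row can be, because the class is named and identifiable at screening.

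**2. Does the prohibition act as an eligibility rule?** Section 12.3 says that "major protocol deviations include deviations from inclusion/exclusion criteria, from concomitant medication restrictions". It counts the two as different kinds of deviation. Section 8.2 governs what may be given and does not say who may enter. A patient who requires a PDE5 inhibitor therefore meets no listed exclusion.

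**3. What happens to that patient after randomization.** The protocol leaves three courses:
- go without the drug until at least 24 hours after the last dose;
- receive it as a deviation, with Medical Monitor review (Section 8.2);
- stop study drug (Section 7.5), after which a permanent stop cannot be reversed.

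**4. Length of the first course.** Inputs: infusions every 12 hours for 7 days, 3 hours each (Section 6.2), and a 24-hour tail (Section 8.2).
- Number of infusions: 7 × 2 = 14.
- Start of infusion 14, counted from the start of infusion 1: 13 × 12 = 156 h.
- End of infusion 14: 156 + 3 = 159 h.
- Earliest end of the prohibition: 159 + 24 = 183 h, and 183 / 24 = 7.6 days.
- Counted from the start of the last infusion instead: 156 + 24 = 180 h = 7.5 days.

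This ignores the ±2-hour dosing window and any holds. It applies in either arm, because dosing is blinded. It measures how long the restriction lasts and is not an estimate of harm.

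**5. Safeguards already in place**
- PDE5 inhibitors are prohibited during dosing and for at least 24 hours afterwards (Section 8.2).
- No infusion starts if mean arterial pressure is below 65 mmHg (Section 9.2).
- Study drug is held, then reduced by 25%, after an acute systolic fall during infusion or within 1 hour of its end that needs a fluid bolus or new or increased vasopressor (Section 9.2).
- Pressure is checked before each infusion, every 30 minutes during it, at its end, and 1, 2 and 4 hours later (Appendix 1, footnote 4).
- The DMC reviews safety after 20 subjects have completed dosing and may recommend stopping if more than 20% of GC4419 subjects must discontinue under the protocol's criteria (Section 14.4).

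These limit the consequences of a pressure fall. None of them keeps a patient with a known need for a prohibited drug from being randomized.

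**The case against.** The strongest reply is that the protection already exists. PDE5 inhibitors are expressly forbidden during dosing, so the omission from exclusion 9 looks like a missing duplicate. Section 8.2 also provides a route for a subject with a real clinical need, and Section 12.3 sends unclear eligibility questions to the Clinical Research Associate and medical ones to the medical monitor.

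Much of this stands, and it is why the point is minor. Two things remain. The Section 8.2 route operates after a prohibited drug has been given. The Section 12.3 route is for criteria that are unclear, whereas exclusion 9 is clear and simply silent on PDE5 inhibitors.

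A reader might infer more than the documents support, in three ways:
- **That a washout rule is missing.** The prohibition states an end but no start, so it could be read as leaving uncovered a dose taken earlier and still acting at the first infusion. But a ban on concomitant use that lasts until 24 hours after the last dose naturally runs from the start of dosing. The documents give no duration of action for any of these drugs, so a meaningful overlap cannot be shown from them. Appendix 1, footnote 10 lets the first two doses be moved only to fit the 12-hourly schedule, so it offers no basis for a washout delay.
- **That subjects are lost to the analysis.** Section 7.5 treats stopping study drug and withdrawing from the study as different things, and Section 11.4 analyses every randomized subject who received at least one dose.
- **That a known share of the 50 subjects is affected.** The documents give no frequency, and none is assumed here.

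**Conclusion.** The mismatch is real and can be read directly from the text: one of two named classes that share a prohibition and a stated reason is missing from the entry criteria. It is minor, a cheap improvement that bears on patient safety only. Its one measurable feature is the period of about 183 hours for which a patient who completes nominal dosing would have to forgo a required PDE5 inhibitor. That figure rests on 14 infusions exactly 12 hours apart with no holds. The number of patients concerned cannot be derived from the documents and may be zero. There is no consequence for the sample size, the primary test or the analysis population.

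**What to change.** Extend exclusion 9, in both the Synopsis and Section 7.2, by adding *or PDE5 inhibitors* after nitrates. Leave the investigator-judged class in Section 8.2, where individual judgement belongs.

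The cost is one phrase in two places. No new data are collected, since concomitant medications are already reviewed at screening. The downside is an occasional exclusion of a patient who requires a PDE5 inhibitor.
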